Following informed consent, patients will be assigned a subject number and randomized to one of the two 7 session interventions (IMCP vs ISP) or to the EUC control condition. Randomization will be completed by MSKCC's Department of Biostatistics. After randomization, participants will be contacted and informed which randomization assignment they received and scheduled for the intervention. The intervention should begin within four weeks of randomization. Patients who cannot begin the intervention within 30 days of consent (because of conflict or illness), will be placed on a waitlist so they can be offered the intervention when they do not have any conflicts at which time patients will be re-consented.

After the patient has been randomized, they will complete a T1-Baseline Assessment (week 1) before the 1st session (see Appendix C). The assessment battery will be re-administered at 3 subsequent points: T2 (midpoint, at session 4, Appendix D); T3 (post-intervention, following the 7th session of the intervention or at the completion of 14 weeks, whichever occurs first, Appendix E) to assess changes over the course of treatment; and T4 (follow-up, 8-12 weeks post completion of T3, Appendix F) to assess maintenance of treatment gains. The EUC sample will also be administered the battery of questionnaires at approximately equivalent intervals. Please see Appendices A, C, D, E, & F and if it is overly burdensome to come to the counseling center for assessments patients will be given the option to complete them by mail, email the blank questionnaires to participants for them to print and complete at home (forms will be returned by mail), or administer the questionnaires over the phone. Figure 3, section 9.0 for specific measures)

All intervention sessions will be conducted at Ambulatory Counseling Center facilities of the MSKCC Department of Psychiatry and Behavioral Sciences or another Memorial Sloan-Kettering Cancer Center treatment facility. However, in rare circumstances if deemed appropriate by the interventionist (e.g., illness, emergency, transportation difficulties) telephone sessions will be permitted. All psychotherapy sessions will be audio recorded to be used for treatment integrity purposes. Portions of these audio recordings may be transcribed for academic, educational, or

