7.1 ASSESSMENT/EVALUATION PLAN

Following completion of the screening assessment (T0), participants will be randomized to one of the 3 study arms (IMCP, ISP, or EUC) and informed of the intervention they have been assigned to receive. The assessment battery described above will be re-administered at four subsequent points (See Figure 3): T1 (baseline, before the intervention, week 1, Appendix C), T2 (midpoint, at session 4, Appendix D); T3 (post-intervention, following the 7th session of the intervention or at the completion of 14 weeks, whichever occurs first, Appendix E) to assess changes over the course of treatment; and T4 (follow-up, 8-12 weeks post completion of T3, Appendix F) to assess maintenance of treatment gains. Patients in the EUC arm will be re-administered the assessment battery at comparable time points. In addition to the T0, T1, T3, and T4 questionnaires, we will be asking patients in the IMCP arm to complete an optional weekly session rating survey (Appendix R). Patients who complete all 5 assessments will be eligible to receive a \$20 Barnes and Noble gift card as a thank you for study completion. This will be delivered to the patient in person, by mail or email, depending on participant preference.

Figure 3: Study Assessment Timeline

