5. Duke-UNC Functional Social Support Questionnaire (FSSQ): As a measure of perceived social support we are utilizing an 11-item multidimensional, functional social support questionnaire (range 0-4). (Broadhead et al., 1988). The Duke-UNC is a reliable and valid self-report instrument that generates a total score representing overall social support, and two subscale scores corresponding to confidant support and affective support. This measure has adequate demonstrated levels of internal consistency and test-test reliability ($> .60$), as well as significant correlations with other measures of social functioning. (5 minutes; T1)
6. Life Orientation Test Revised (LOT-R): This 8-item measure of optimism has been widely used in studies of adjustment to stress and illness and depression (range 8-56). Studies have demonstrated high levels of reliability (e.g., alpha coefficients ranging from =.76-.80 and test-retest reliability of .79) as well as concurrent and discriminant validity (Scheier & Carver, 1985). While most studies have treated the LOT-R as a trait-like measure (dispositional optimism), Carver et al. (1993) found that LOT-R scores were influenced by situational stress in a sample of women with breast cancer. (2 minutes; T1)

Measures of Psychotherapy Preference, Process and Adherence:

1. Pre-Randomization Preference Questionnaire (PRP): A face valid questionnaire developed by the investigators to assess patients' preference for interest in participating in a psychotherapy intervention, and preferences regarding content and group assignment. Patients are asked to rate (on a 0-4 Likert-type scale) their preferences for 3 aspects of psychotherapy content: a) social support, b) expression of feelings, c) finding a sense of meaning and purpose in life. Patients are also being asked to indicate their preference for the meaning-centered vs. supportive psychotherapy vs. enhanced

usual care study arms (they are told that this information is solely for analytic purposes and will not influence group assignment). (1 minute; PR)

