Analyses: Putative explanatory covariates will be identified and tested statistically using the method originally described by Baron and Kenny (1986), and more recently by MacKinnon (2008). Specifically, these will involve Multi-Variate Analysis of Covariance (MANCOVA) using the changes in the six primary outcomes (post intervention minus baseline) as a function of intervention condition, controlling as covariates the effects of gender, race/ethnicity, and baseline covariates in religiosity, social support, optimism, physical symptom burden, pain severity, and overall symptom burden. This analytic approach entails the following advantages: 1) change scores have the advantage of clearly identifiable direction of change, 2) psychosocial outcomes are measured on an interval scale (such as measures of temperature in the Fahrenheit or Celsius scales), so that change scores are less prone to problems associated with respondents using different internal psychological scales; and 3) precedence exists (Flay et al. 1995) in interventions designed for behavioral change. This method offers several advantages, both in terms of power as well as interpretation, to a traditional repeated measures design for analyzing data when both independent and dependent variables are assessed at two or more time points (Huck & McLean, 1975; Willet, 1988-9). Change score analyses will include the baseline score as a covariate if change is significantly correlated with baseline score (as is often the case).

To assess the relative impact of Individual Meaning-Centered Psychotherapy on different aspects of meaning (e.g., purpose, coherence, existential vacuum), as well as on different aspects of spiritual well-being (meaning versus faith):

Two additional MANOVA models will be carried out. In the first model, pre-post change scores of different aspects of meaning (e.g., purpose, coherence, existential vacuum) will be modeled by intervention conditions to examine the relative impact of IMCP on these outcomes. The canonical weights will be used to estimate the relative contribution of each mean components on the overall canonical function. Components of spiritual well-being will also be analyzed similarly, in a separate MANOVA model. Univariate ANOVA contrasts will be used to compare IMCP against ISP and IMCP against EUC.

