12.3 Randomization

Participants will be randomized to one of the two 7-week interventions (Individual Meaning Centered Psychotherapy or Supportive Individual Psychotherapy) or the Enhanced Usual Care. After eligibility is confirmed and immediately after consent is obtained, patients will be registered in the MSKCC Protocol Participant Registration (PPR) system and randomized using the MSKCC Clinical Research Database (CRDB), by calling the MSKCC PPR Office at [contact] between the hours of 8:30 am and 5:30 pm, Monday - Friday.

Randomization is overseen by the MSKCC Biostatistics Service. Randomization will be accomplished by the method of random permuted block, and stratified by two dichotomized variables: 1) baseline Distress Thermometer (4 through 6 vs. 7 through 10); and 2) baseline Karnofsky score (60 through 79 vs. 80 or greater).

Patients who are registered and randomized, but cannot make their scheduled session time (because of conflict or illness) will be placed on a waitlist so they can be offered a spot when they are available in the future, in the same treatment assignment as randomized.

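### The T1 self-report battery is completed after patients know their arm, so secondary and missing-data analyses that use T1 can carry a reaction to assignment; the primary MANOVA on observed scores does not

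*Combined protocol and SAP*

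**What the plan says.** **Order of events.**
- Section 12.3 places registration and randomization directly after consent: "After eligibility is confirmed and immediately after consent is obtained, patients will be registered".
- Section 4.2 then has the arm disclosed: "After randomization, participants will be contacted and informed which randomization assignment they received and scheduled for the intervention". The baseline follows: "After the patient has been randomized, they will complete a T1-Baseline Assessment (week 1) before the 1st session".
- Section 7.1 agrees: once screened, patients are allocated to an arm and "informed of the intervention they have been assigned to receive". Next in its list comes "T1 (baseline, before the intervention, week 1, Appendix C").
- The schedule in Section 9.1 shows screening and randomization at week 0 and T1 at week 1.

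**Use of T1.** Under the secondary aims in Section 11.0, the moderator analysis is a MANCOVA "using the changes in the six primary outcomes (post intervention minus baseline"), with further baseline covariates. The analyses of aspects of meaning and of spiritual well-being use pre-post change. The mediation model uses week-15 change adjusted for change in LAP-R. One missing-data analysis assumes no change in patients who dropped out.

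**Preference.** Before randomization the plan records which arm each patient would like: "Patients are also being asked to indicate their preference for the meaning-centered vs. supportive psychotherapy" or enhanced usual care (Section 7.1).

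**The concern.** A baseline used in a change score, or as a covariate in an arm comparison, should be a value that assignment cannot have influenced. Here T1 is taken when the patient already knows the arm. Blinding is not possible, entry requires a Distress Thermometer score of 4 or more, and the scales are self-reports of mood, hopelessness and meaning. Some patients will have received the arm they wanted and others will not. Relief or disappointment could therefore shift T1 scores differently by arm. EUC has no first session before which to place T1, and Section 9.1 puts its referral contact in the same week as T1.

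At stake are the arm contrasts that subtract or adjust for T1, and the completeness of T1 itself: a patient who leaves on learning the arm has no T1 scale scores, and such losses may differ between arms.

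**Working it through.** The plan gives no figure on this point, so there is none to reproduce. The check covers the order of events, the analyses that use T1, and what a T1 shift would do to them.

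**1. Is there an earlier measurement?** Section 7.1 speaks of the battery being re-administered from T1 on, which could suggest a T0 administration. The timing codes in its measure list rule this out. LAP-R, FACIT-Sp, HADS, SAHD, HAI and MQOL are coded T1–T4, IE-12, FSSQ and LOT-R T1 only, and MSAS T1, T3 and T4. The order is therefore T0, consent, randomization, disclosure, T1, session 1. No section withholds the assignment until T1 is done.

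**2. Which analyses use T1?**

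| Analysis (Section 11.0) | Use of T1 |
|---|---|
| Primary omnibus MANOVA | None: post-intervention scores, arm as only predictor |
| Moderator MANCOVA | Change in six outcomes; religiosity, social support, optimism and symptom covariates; outcome baseline if correlated with change |
| Aspects of meaning and of spiritual well-being | Pre-post change |
| Mediation | Outcome change and LAP-R change |
| No-change analysis for dropouts | T1 stands in for the missing score |
| Multiple imputation | Only if T1 scores enter the imputation model, which is not specified |

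Gender, race/ethnicity, screening Distress Thermometer, screening Karnofsky and treatment preference are collected before randomization and cannot be affected.

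**3. Bias formulas.** Let disclosure create a T1 difference of δ SD between two arms, and let ρ be the T1–T3 correlation, with equal SDs.
- Post-only contrast: bias 0.
- Change score: (T3 difference) − (T1 difference), so bias −δ.
- T1-adjusted contrast: (T3 difference) − ρ × (T1 difference), so bias −ρδ.

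The documents give neither δ nor ρ. Assuming δ = 0.05–0.20 and ρ = 0.6, the bias is 0.05–0.20 SD for change scores, and 0.6 × 0.05 = 0.03 to 0.6 × 0.20 = 0.12 SD with adjustment.

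**4. False-positive rate for one scale and two arms.** Assume n = 104 per arm (the plan's week-7 number), no true T3 difference, two-sided 0.05 and a normal approximation. The standard errors are √[2(1−ρ)]·√(2/n) for change and √(1−ρ²)·√(2/n) with adjustment. The rate is 1 − Φ(1.96 − b/SE) + Φ(−1.96 − b/SE), where b is the absolute bias.

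Example with ρ = 0.5 and δ = 0.10: √(2/104) = 0.139. For change, SE = 0.139, b/SE = 0.72 and the rate is 11.1%. With adjustment, b = 0.05, SE = 0.120, b/SE = 0.42 and the rate is 7.0%.

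| δ (SD) | Change score, ρ 0.3–0.7 | T1-adjusted, ρ 0.3–0.7 | Post-only |
|---|---|---|---|
| 0.05 | 6–8% | 5–6% | 5% |
| 0.10 | 9–15% | 6–11% | 5% |
| 0.20 | 23–46% | 7–29% | 5% |

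**5. Direction.** Take scores as higher = better. If T1 is worse in EUC from disappointment, EUC appears to improve more, and change scores understate IMCP against EUC. The no-change analysis works the other way on post-intervention scores: with the plan's 25% attrition, equal in both arms, carrying T1 forward moves the contrast by 0.25 × δ in favour of IMCP.

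**The case against.** **The primary analysis is not exposed.** A reader might infer from the order of assessments that the trial's main comparison is biased. The documents do not support that: the primary MANOVA on observed week-7 scores contains no T1 value. T1 can reach the primary outcomes only through missing-data handling. This stands in full.

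**Not every baseline covariate is affected.** Those collected at T0 are safe, and Section 7.1 notes that optimism (LOT-R) is usually treated as a trait, though it also cites a study in which it responded to stress. Patients who leave early likewise keep their T0 data; what they lack is T1 scale scores. This stands.

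**The size is conjecture.** It is also tempting to set the bias against the 0.20 in the sample-size section. That figure is a difference in canonical variates used to size the primary test, not a planned difference in single-scale change, so the comparison is not valid. For IMCP against ISP, both arms receive equally many sessions of equal length, so a reaction to therapy versus no therapy should largely cancel. A uniform shift would not alter an arm-by-moderator interaction, but the moderator model as written describes arm effects with covariates. The δ formulas are not derived for the mediation model, where T1 enters on both sides. These limits stand; they restrict what can be said about size, not the order of events.

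**Measuring close to session 1 is defensible** in patients whose health may deteriorate, and the battery takes about an hour. This is a real trade-off, but it does not require patients to know their arm first.

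**Conclusion.** The concern holds for the T1-dependent analyses: the change scores and T1-measured covariates under all three secondary aims, the no-change analysis, and any imputation that uses T1. These rest on values taken after unblinded patients knew their arm, and T1 scores may be missing unequally by arm. The primary MANOVA on observed scores and the T0 covariates are not affected.

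The order of events is certain. That a reaction occurs, how large it is and which way it acts are not shown. If it shifts T1 by δ SD between arms, change-score contrasts move by δ and T1-adjusted contrasts by ρδ. The numerical ranges above rest entirely on assumed δ and ρ. The reason to act is that a pre-assignment value cannot be recovered afterwards, while obtaining one needs only a change of order.

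**What to change.** Amend Sections 4.2, 7.1 and 12.3 so that in all arms the order is consent, T1 self-report battery, randomization, disclosure. At minimum, require T1 to be complete before the arm is disclosed. Bring the Section 9.1 schedule and the T1 timing in Section 1.0 into line.

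- Use the mail, email or telephone completion that Section 4.2 already allows. Section 7.1 describes mail and telephone only for follow-up questionnaires, so extend that wording to T1.
- Leave until after assignment the two T1 items that need a therapist: the WAI-SF (not given in EUC) and the therapist-rated part of prognostic awareness.

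The sample size and the instruments do not change. The costs are the wording, some delay between consent and randomization, a baseline up to about 30 days before session 1 (longer for waitlisted patients), and a few patients who complete T1 but are never randomized. That last loss cannot depend on the arm.

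If the order cannot be changed, report T1 scores and T1 completeness by arm, and base the secondary arm contrasts on post-intervention scores adjusted only for T0 variables.

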8.0 TOXICITIES/SIDE EFFECTS

Minimal risk of psychological distress is posed by study questions that ask participants to identify their current problems. However, since study items were chosen to reflect what are likely to be

existing concerns, the present study is not expected to markedly increase participants' psychological distress above their routine concerns. Experienced personnel, trained in interviewing medically ill individuals, will administer all instruments, and will be supervised by the Principal Investigator or Project Coordinator. Participants' reactions will be observed and signs of significant distress will be followed up by the PI or study therapist with attention to presence of any serious psychological concerns. In the unlikely event of significant acute distress, participants will be referred to a staff member from the Department of Psychiatry and Behavioral Sciences. If a research participant indicates that s/he is acutely suicidal and poses a significant and acute risk of self-harm, this information will be shared with their attending physician so that timely and appropriate psychiatric assessment and care can be provided by the MSKCC Social Work or Psychiatry Service staff.

However, some subjects may become distressed or experience anxiety when discussing end-of-life care issues in the individual psychotherapy sessions or in response to filling out the self-report questionnaires that inquire about their illness, degree of depression, thoughts on end of life care, feelings of hopelessness, pain and physical symptoms, quality of life and social support. All patients will be monitored for severe distress and explicit suicidal ideation with plan or intent at each assessment point (including EUC). We will continue to utilize interviewers who have been trained to be sensitive to the nature of end-of-life care issues. When necessary, subjects who experience psychological distress related to filling out self-report questionnaires will be referred to appropriate care by the MSKCC Psychiatry Service.

There will be only one exception to the strict patient confidentiality policy, described above, which pertains to information obtained during the research assessment, which would indicate that the patient is seriously suicidal and may pose a significant and acute risk of self-harm. Subjects will be informed of this exception, and will also be informed that such information will be shared with the P.I. of the study and their attending physician so that timely and appropriate psychiatric assessment and care can be provided by the MSKCC Psychiatry Service.

There is a slight risk that participants may become fatigued or uncomfortable during the course of the self-report assessment. The assessment protocol has been designed to be as brief as possible in order to gather the required information. If necessary, the questionnaires will be read to the participant. The questionnaires should take approximately one hour to complete.

Expected Frequency of Side Effects/ Toxicity

In our previous studies involving over 500 cancer patients, using a very similar battery of questionnaires and assessment tools examining such issues as depression, hopelessness, suicidal ideation, pain, quality of life, etc., we have encountered little resultant emotional distress. Subjects in fact reported that they were relieved to be discussing such issues. We will, however, continue to utilize research personnel who have been clinically trained to be sensitive to issues of emotional distress, fatigue and subject burden.

9.1 PRIMARY OUTCOMES

The primary outcomes to be measured include measures of meaning (LAP-R), spiritual well-being (FACIT-Sp) and psychological distress (HADS, SAHD, HAI, MQOL). Specific measures are described above in section 7.0 and assessment timeline described below.

Week	0	1	2	3	4	5	6	7	15
Screening and Randomization to Intervention	x								
Assessments	T ₀	T ₁			T ₂			T ₃	T ₄
Interventions:									
Meaning Centered Psychotherapy (1 hour sessions)		x	x	x	x	x	x	x	
Supportive Psychotherapy (1 hour sessions)		x	x	x	x	x	x	x	
Enhanced Usual Care (Referral Facilitation)		x			x			x	

10.0 CRITERIA FOR REMOVAL FROM STUDY

Given the clinical course of patients with advanced cancer, not all patients entered into the study are expected to complete the entire trial. Subjects will be taken off study protocol under the following circumstances:

- Patient voluntarily withdraws from study
- Onset of severe cognitive difficulties that preclude participation in the intervention or accurate assessment in the judgment of the therapist and the P.I.
- Patient is unable to tolerate the intervention in the judgment of the therapist and the P.I.
- Infectious episode that is of sufficient severity to preclude further participation in the study.
- Non-compliance with the intervention without medical cause or reasonable explanation in the judgment of the therapist and the P.I.

11.0 BIOSTATISTICS

This project involves a parallel-arm randomized controlled clinical trial to compare the efficacy of three psychotherapy interventions: 1) Individual Meaning-Centered Psychotherapy (IMCP); 2) Supportive Individual Psychotherapy (ISP); and 3) Enhanced Usual Care arm (EUC). We plan to recruit altogether 414 patients (138 in each arm) with solid tumors with advanced disease. The primary outcomes include assessments of meaning (LAP-R), spiritual well-being (FACIT-Sp) and psychological distress (HADS, SAHD, HAI, MQOL).

Omnibus MANOVA for the primary aim:

The general paradigm for assessing the outcomes will be multivariate analysis of variance (MANOVA). MANOVA is appropriate because the primary psychosocial outcomes are highly correlated. The MANOVA method essentially combines the multiple dependent variables together into a weighted linear combination of canonical variates. The canonical coefficients provide the weights in this linear combination. The canonical weights have several advantages. The main advantage is that they inform the relative contribution of each outcome to the overall canonical function (i.e., whether or not meaning contributes more than spiritual well-being to the overall canonical function). MANOVA was chosen, rather than, for example, a mixed-effects modeling approach, primarily because of these considerations. In MANOVA, the combined canonical variate is analyzed in a manner similar to a univariate ANOVA.

The primary aim of this study will be evaluated in one omnibus, one-way MANOVA model against the null hypothesis that all three randomized arms entail comparable post-intervention outcomes in meaning, spiritual well-being, and psychological distress. Thus, the dependent variables will be the six primary outcome assessments (LAP-R, FACIT-Sp, HADS, SAHD, HAI, and MQOL) measured at the post-intervention time point (week 7). The sole independent variable is the randomized intervention assignment. Dunlop, Cortina, Vaslow & Burke (1996) showed that this method provides the most generalizable findings, findings that do not depend on the patients' baseline scores or other baseline characteristics. Thus, the omnibus MANOVA will test whether or not the psychotherapy groups differ in all six correlated outcomes of interest.

The T2 (mid-intervention) assessments are made because some patients may be too sick to complete the 7-session intervention. For these patients, we will use the T2 assessment to represent the most available data on intervention effect.

Sample size and statistical power considerations:

Two important hypotheses need to be established in this trial: 1) IMCP is superior to EUC; and more importantly, 2) IMCP is superior to ISP for improving psychosocial outcomes in patients with advanced cancer. Therefore, we have based sample size considerations on sufficient statistical power to detect these two differences. We have conservatively based our sample size calculations on a 0.20 standardized mean difference in the MANOVA canonical variates between the IMCP and ISP interventions. This 0.20 difference is what Cohen would consider a —small effect size in psychosocial research (Cohen, 1992), representing subtle group differences typically observed in psychotherapy clinical trials. Cohen (1992) distilled the findings of decades of psychosocial research and arrived at a classification of a —small effect (0.20 standardized mean difference), a —medium effect (0.50 difference), and a —large effect (0.80+ difference). This —small difference is also a sensible assumption, due in part to the small group differences in some of the psychosocial outcomes in our pilot IMCP trial (Table 1, e.g., psychological distress). Thus, we planned to have a sufficiently large sample size to detect subtle differences. Overall, this conservative estimate would accommodate outcomes in psychological distress which our pilot data showed a small difference. Based on these assumptions, we would need 104 participants in each arm at post-intervention (week 7) in order to obtain a power of 0.80. Other assumptions that go into this estimation included two *a priori* contrasts (IMCP vs. EUC and IMCP vs. ISP), and a two-sided, type-I error rate of 0.01 in the MANOVA test. The statistical power calculations were obtained from the computer program G*Power version 3.1 (Faul, Erdfelder, Lang & Buchner, 2007), for a MANOVA model with six correlated outcome variables. The output of the G*Power estimate is included below.

F tests – MANOVA: Global effects

Options : Pillai V, O'Brien–Shieh Algorithm

Analysis : A priori: Compute required sample size

Input:	Effect size $f^2(V)$	= 0.20
	α err prob	= 0.01
	Power (1– β err prob)	= 0.80
	Number of groups	= 2
	Response variables	= 6
Output:	Noncentrality parameter λ	= 20.8000000
	Critical F	= 2.9936309
	Sample size	= 104
	Actual power	= 0.8062691
	Pillai V	= 0.1666667

A sample size of 104 per randomization arm (138 at baseline) at post-intervention would accommodate a post-intervention attrition rate of up to 25%, which is within the attrition rate in our pilot IMCP trial. The estimated sample size at the follow-up time point (week 15) is 90 participants per intervention condition.

Based on our current IMCP Group psychotherapy intervention, we are currently recruiting at a rate of 5 – 6 individuals to participate. This study involves the IMCP individual therapy, which is more flexible in terms of enrolling patients quickly and scheduling for starting of the therapy sessions. Thus we are confident that we will be able to recruit at a rate of 8 – 9 individuals per month and complete the total enrollment of 414 within the 4-year recruitment period.

Data analytic plans for the secondary aims

To examine clinical and demographic variables that may correspond to differential responses to Individual Meaning-Centered Psychotherapy (e.g., potential moderating influences such as gender, race/ethnicity, religiosity, level of pre-intervention social support, optimism, physical symptom burden, prognostic awareness, and treatment dose).

We anticipate that several socio-demographic and clinical variables will moderate the impact of IMCP. For example, we expect that level of religiosity (based on the IE-12) at the baseline/pre-intervention assessment will be inversely related to treatment response (i.e., less religious individuals will be more likely to experience benefits from this intervention than more religious individuals). We also predict that level of social support will moderate improvement, with those patients reporting higher levels of social support receiving the greatest benefits (because of the emphasis on connectedness to others as a source of meaning in the IMCP intervention). On the other hand, we expect that patients with poorer physical functioning (e.g., lower Karnofsky score), greater pain severity and overall symptom burden (MSAS Global Distress Index scores) will be less likely to benefit from the interventions, in part because unmanaged physical symptoms may impede participation.

Analyses: Putative explanatory covariates will be identified and tested statistically using the method originally described by Baron and Kenny (1986), and more recently by MacKinnon (2008). Specifically, these will involve Multi-Variate Analysis of Covariance (MANCOVA) using the changes in the six primary outcomes (post intervention minus baseline) as a function of intervention condition, controlling as covariates the effects of gender, race/ethnicity, and baseline covariates in religiosity, social support, optimism, physical symptom burden, pain severity, and overall symptom burden. This analytic approach entails the following advantages: 1) change scores have the advantage of clearly identifiable direction of change, 2) psychosocial outcomes are measured on an interval scale (such as measures of temperature in the Fahrenheit or Celsius scales), so that change scores are less prone to problems associated with respondents using different internal psychological scales; and 3) precedence exists (Flay et al. 1995) in interventions designed for behavioral change. This method offers several advantages, both in terms of power as well as interpretation, to a traditional repeated measures design for analyzing data when both independent and dependent variables are assessed at two or more time points (Huck & McLean, 1975; Willet, 1988-9). Change score analyses will include the baseline score as a covariate if change is significantly correlated with baseline score (as is often the case).

To assess the relative impact of Individual Meaning-Centered Psychotherapy on different aspects of meaning (e.g., purpose, coherence, existential vacuum), as well as on different aspects of spiritual well-being (meaning versus faith):

Two additional MANOVA models will be carried out. In the first model, pre-post change scores of different aspects of meaning (e.g., purpose, coherence, existential vacuum) will be modeled by intervention conditions to examine the relative impact of IMCP on these outcomes. The canonical weights will be used to estimate the relative contribution of each mean components on the overall canonical function. Components of spiritual well-being will also be analyzed similarly, in a separate MANOVA model. Univariate ANOVA contrasts will be used to compare IMCP against ISP and IMCP against EUC.

To explore whether an enhanced sense of meaning —explains (mediates) improved psychological well-being (i.e., increased quality of life, decreased psychological distress):

This mediation analysis will be carried out using a MANCOVA model. The dependent variables will be the changes in psychosocial outcomes at the follow-up assessment time point (week 15 minus baseline) in quality of life and psychological distress as a function of intervention condition, adjusting for the post-intervention change in meaning (post-intervention LAP-R minus baseline LAP-R). Thus, the follow-up outcomes will be predicted by enhanced sense of post-intervention meaning. This lagged analysis is necessary because there is a potential confounding effect, for example, in using the post-intervention changes in meaning in predicting post-intervention quality of life. The lagged analysis between follow-up outcomes in quality of life and psychological distress and post-intervention changes in meaning preserves a plausible temporal ordering of causes and effects.

Intent-to-treat analyses and handling of missing data:

Intent-to-treat (ITT) analysis is the gold standard in evaluating the relative efficacy of therapeutic regimes for patients assigned to different treatment arms whether or not they comply with the full treatment plan as defined in the protocol. In contrast to studies that assess clinical outcomes that are observable whether or not patients comply with therapy, it is likely in this study that patients who fail to participate in particular counseling sessions will also be missing the corresponding outcome data. Thus, examination and imputation of incomplete data will be an integral part of our ITT analysis. Data for intermediate time points might be imputable by one of several available statistical techniques. However, it is more problematic to assess outcomes for patients who essentially drop out of the study, namely, who are missing the final (and possibly preceding) evaluations. Although we shall endeavor to obtain final evaluation-time data even for patients who discontinue the counseling, but because of the likelihood that premature withdrawal is related to deteriorating physical health, we cannot rely on this and will therefore use appropriate statistical methods. One preferred approach is the Pattern-Mixture Model (Hedeker & Gibbons, 1997), which assumes that patients can be grouped into a small number of implicit cohorts with different patterns of missing data. This method models the trajectories of responses within each cohort and combines results across cohorts to make overall comparisons between treatment arms. The Pattern-Mixture Model can be relatively easily applied in practice using a publicly accessible SAS macro. This approach will handle two potential, inter-related issues, namely, intent-to-treat analysis and missing data while making a global assessment of the overall efficacy of the two types of counseling. We anticipate that the majority of patients will complete most or all of the planned sessions and the corresponding assessments. However, our pilot data suggest that there may be sufficient attrition to warrant use of the above-described approach even if drop-out rates do not differ significantly between the two treatment arms.

Missing data:

Because attrition may significantly impact the MANOVA, we will utilize several techniques for dealing with missing data (Nich & Carroll, 1997; Singer & Willett, 1991). These techniques may

include estimating missing data, complete data analysis, and intention to treat analysis. Although missing data can be estimated using a number of powerful techniques (Graham, Hofer, Donaldson, MacKinnon & Schafer, 1997), we intend to use a multiple imputation procedure described by Schafer and Olsen (1997), which is capable of handling categorical data, continuous data, and any combination of the two. Graham et al. (1997) have argued that parameter estimates using this method are unbiased and have standard errors that are typically only slightly larger than those generated by other methods. In order to assess the effect of this imputation method, we will compare results based on imputed data to those based only on subjects who completed the study (this comparison allows for an assessment of the extent to which biases may have influenced study results). Finally, we can analyze data assuming that those subjects who dropped out of treatment had no change in either meaning or psychological distress.

Procedures to control False Discovery Rate (FDR):

One final issue is that of multiple statistical analyses. While the use of MANOVA models decreases the possibility of inflated type I error normally observed when several outcome measures are being evaluated, analysis of the individual dependent variables can also incorporate a multiple comparisons method, such as a the False Discovery Rate-controlling procedure (Benjamini & Hochberg, 1995).

